#### 2.4 Sample Size Determination

To test the primary hypothesis for the proof of concept, an alternating logistic regression will be used to compare the proportion of live female adult worms without *Wolbachia* at Month 6 between each of the four active arms (Arm A, B, C, or D) and the control arm (Arm E), taking into account the clustering of this worm-level endpoint by subject. Using simulations that add substantial clustering by subject to the endpoint values and assuming the number of worms in each subject varies from 1 to 10, following the multinomial distribution with probability = (0.20, 0.16, 0.16, 0.16, 0.08, 0.08, 0.08, 0.03, 0.03, 0.02) for values (1, 2, 3, 4, 5, 6, 7, 8, 9, 10), 17 subjects will provide 88% power to detect the difference between an active arm (Arm A, B, C, or D) where 70% of worms are without *Wolbachia* (2-sided  $\alpha = 0.10$ ). The clustering of the endpoint values by subject is provided by the Pearson intraclass correlation coefficient (ICC) for binary outcomes and was given as ICC = 0.54 for simulated arms where 70% or 30% of the worms are without *Wolbachia*.

To test the primary hypothesis for the combination rule, an alternating logistic regression will be used to compare the proportion of live female adult worms without *Wolbachia* at Month 6 between the combination arm (Arm C or D) and the two single drug arms (Arm A and E) separately, 25 subjects per arm will provide 81% power to detect the difference between the combination arm where 90% of worms are without *Wolbachia* and the single drug arm where 70% of worms are without *Wolbachia* (2-sided  $\alpha = 0.10$ ). ICC = 0.54 was added to the simulated arm where 70% of the worms are without *Wolbachia*. Minimal clustering (ICC = 0.01) was added to the simulated arm where 90% of the simulated arm where 90% of the worms are without *Wolbachia* because there would be little variation among subjects with an overall high response rate. 30 subjects will be enrolled per arm to account for 17% drop out by Month 6.

# 3.0 Endpoints

# 3.1 Primary Endpoint

The primary efficacy endpoint is the status of each live female adult worm as without *Wolbachia*, assessed by immunohistology of nodules collected after nodulectomy at Month 6.

## 3.2 Secondary Endpoints

There is no key secondary endpoint in Part 1 of Study B18-894/DNDi-TYL-01. The other secondary efficacy endpoints are:

- the proportion of live female adult worms with only degenerated embryos in the uterus per subject after nodulectomy at Month 6;
- the proportion of live female adult worms out of all female adult worms per subject after nodulectomy at Month 6;
- the absence of microfilariae in nodular tissue per subject after nodulectomy at Month 6;
- the status of each subject as without skin microfilariae at Months 3 and 6;

- the reduction from baseline in skin microfilarial density (defined as the mean number of microfilariae/mg per subject) at Months 3 and 6;
- the status of each nodule that contains at least 1 live female adult worm as without *Wolbachia* assessed by PCR at Month 6.

#### 3.3 Exploratory Endpoints

The exploratory efficacy endpoints are:

- the absence of *Wolbachia* in skin microfilariae per subject by PCR at all timepoints;
- the decline from baseline in number of *Wolbachia* (assessed by PCR) in skin microfilariae per subject at all timepoints;
- microfilaria levels in the cornea and anterior chamber per subject, at all timepoints when ophthalmological assessments are performed;
- the presence, severity and clinical evolution of onchocerciasis ocular disease and onchocerciasis skin disease in each subject at all timepoints when ophthalmological or skin examinations are performed.

#### 3.4 Safety Endpoints

The safety endpoints are based on the following assessments:

- Adverse Event (AE) assessment (all reported AEs);
- Vital signs;
- 12-lead ECG;
- Clinical laboratory parameters: hematology and biochemistry.

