- 10. Clinically significant history of cardiac abnormality, and/or relevant pathological abnormalities in the ECG in the screening period, such as atrioventricular block (PR interval > 240 msec), or prolongation of the QRS complex > 120 msec or QTcF interval > 450 msec.
- 11. Abnormal laboratory test results at Screening, defined as:
 - i. Aspartate aminotransferase/serum glutamic oxaloacetic transaminase and/or alanine aminotransferase/serum glutamic pyruvic transaminase
 2 x upper limit of normal (ULN) and/or total bilirubin > 1.5 x ULN;
 - ii. Serum potassium < lower limit of normal;
 - iii. Serum creatinine > ULN and estimated glomerular filtration rate < 60 mL/min (using the Modification of Diet in Renal Disease equation)
- 12. History of severe drug allergy, non-allergic drug reactions, severe adverse reaction to any drug, or multiple drug allergies.

	Tea
	13. Known hypersensitivity to any ingredient of the IMPs, including the
	active ingredient of ABBV-4083, macrolides, albendazole or to
	ivermectin or to any medication used during the study (e.g. for eye
	examination). 14. Blood donation within 8 weeks prior to Screening or blood transfusion
	received within 1 year prior to Screening.
	15. Coincidental infection with high Loa loa load (> 8000 microfilariae/mL)
	at Screening.
	16. Current hyperreactive onchodermatitis or severe manifestation due to
	onchocerciasis.
	17. Any other past or current condition that the Investigator feels would
	exclude the subject from the study or place the subject at undue risk.
	18. For women of child-bearing potential: pregnant, based on date of last
	menstrual period, and pregnancy test prior to first intake of IMP, or
	breastfeeding.
	19. Unwilling or unable to comply with the requirements of the study protocol
	for the entire duration of the study, in the opinion of the Investigator.
	20. Unable to participate in the study as per local law, if applicable.
Type of Control	In part 1: active control: albendazole
Type of control	In Part 2, base scenario: placebo control
	In Part 2, alternate scenario: active control: ABBV-4083
Study Duration	In Part 1: each subject's participation will last approximately 6½ months,
·	excluding the screening period, which may be up to 8 weeks.
	In Part 2: each subject's participation will last approximately 24½ months, excluding the screening period, which may be up to 8 weeks.
	An independent Data and Safety Monitoring Board will be established by the

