6.1 Inclusion Criteria

To be eligible for the study, subjects must satisfy all of the following inclusion criteria.

1. Written, signed (or thumb-printed) and dated informed consent, after having the opportunity to discuss the study with the Investigator or a delegate.

- 2. Men and women with *Onchocerca volvulus* infection, 18 to 65 years of age inclusive at time of Screening:
 - i. Presence of at least one excisable subcutaneous nodule/onchocercoma detected on palpation;
 - ii. *O. volvulus* infection diagnosed by skin snip method: documented mf-positivity on skin assessment on at least 2 out of 4 skin snips.
- 3. Body weight > 40 kg at Screening.
- 4. For women of child-bearing potential (WOCBP), (see Section 8.2), acceptance of the requirement to use a highly effective form of birth control (see Section 8.2 and Appendix 7) effective from Day 0 until at least 1 month after the final intake of IMP (Part 1: day 43; Part 2: 1 month after the administration of ivermectin or matching placebo at the Month 6 visit). Choice of birth control method must be clearly documented.

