9.3.4.5 Adverse Event Reporting Period

In this protocol, the reporting period is different for AEs and for SAEs:

- Non-serious AEs: all non-serious AEs will be reported from administration of the first intake of IMP until the subject's end of study participation (see Section 3.4). Furthermore, non-serious events that occur in the screening period (from signature of the ICF) until before the first intake of the IMP and that are judged as related to study participation (e.g. haematoma due to venipuncture, wound infection due to skin snips), will be recorded on the AE page of the eCRF.
- SAEs: all SAEs must be reported after signature of the ICF during the screening period until the subject's end of study participation (as defined in Section 3.4) on the AE page of the eCRF and the SAE form.

All treatment emergent AEs that occur during the AE reporting period as defined in this section must be reported, whether or not the event is considered treatment related.

In addition, any SAE that occurs after the end of the AE reporting period and that the Investigator assesses as possibly, probably or definitely related to the IMP or to participation in the study may also be reported as an SAE.

Screening failure: beyond the date of screening failure (to be recorded), only serious study-related events will be reported.

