10.8 Statistical Analysis of Safety

All safety analyses will be performed on the Safety Population, which consists of all subjects who received at least one dose of IMP. Safety will be assessed by AEs, laboratory tests, vital signs, and ECG variables. Details of the analyses will be provided in the Statistical Analysis Plan.

AEs will be coded using the Medical Dictionary for Regulatory Activities (MedDRA). A TEAE is defined as an AE with an onset date that is after the first intake of IMP and no more than 30 days after the last intake of IMP. The number and percentage of subjects experiencing TEAEs will be tabulated using MedDRA system-organ class and preferred term, as well as by severity and by relationship to the IMP as assessed by the Investigator. Summaries of SAEs, deaths, AEs leading to discontinuation will also be provided.

For laboratory test and vital signs variables, mean change from baseline and percentage of subjects with on-treatment laboratory values of CTCAE 5.0 adapted scale grade 3 or 4 will be summarised.

10.9 Interim Analysis of Part 1 and DSMB Recommendation to Proceed to Part 2

Once subjects in Part 1 have completed or prematurely discontinued the study, up to and including nodulectomy at 6 months, a database lock for Part 1 database and an interim analysis of data from Part 1 will be conducted by the Sponsor and the randomisation code unblinded. The unblinded data will be reviewed by the Sponsor and the DSMB (see Section 13.3), for futility and risk/benefit ratio. Taking into account the recommendations of the DSMB, especially regarding the safety assessment of the data, the Sponsor will decide whether or not to proceed to Part 2, and with which dose regimens.

Selection of up to two acceptable/suitable doses / regimens for Part 2 will be based on analysis of all of available unblinded data from Part 1, including safety and tolerability of ABBV-4083 and ABBV-4083 + albendazole, *Wolbachia* depletion, disruption of embryogenesis and an exploratory surrogate marker, microfilaria *Wolbachia*, observed at Months 3 and 6.

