- 11. The Investigator will arrange for a highly effective form of birth control (as detailed in Section 8.2) if required. Must be discussed at screening and checked within 2 days prior to the first intake of IMP and checked at the time-points indicated and documented. In the event of delayed menstrual period for over one month between menstruations, confirmation of absence of pregnancy with a pregnancy test is mandatory. This recommendation also applies to WOCBP with infrequent or irregular menstrual cycles.
- 12. Supine blood pressure (SBP, DBP), supine heart rate, respiratory rate and temperature.
- 13. Ophthalmological findings from examinations including ocular symptoms, ocular examinations including ocular alignment, mobility and pupillary response, visual function (visual acuity, visual field, colour vision), retinal examination and fundus photography, slit lamp examination of anterior and posterior segment and intraocular pressure. Eye microfilarial count and data for clinical outcomes in the eye will be recorded during the ophthalmological examination.
- 14. Assessments for clinical outcomes in the skin (see Study Operations Manual for details) to be performed during physical examinations where the time-points coincide.
- 15. ECGs will be recorded in triplicate (with 1 minute between recordings) except at D3, which will be single. ECGs will be performed 1-2 hours after intake of the IMP. ECG at early termination is only applicable if early termination is before Month 3.
- 16. Blood and urine samples for clinical laboratory safety tests (haematology, biochemistry, & urinalysis (plus urine microscopy where indicated if urinalysis is abnormal and clinically significant).
- 17. IMPs will be administered daily from D0 to D13 on site. IMPs dispensation will be done on D0, D3 and D7 via the IRT system.
- 18.Administration of ivermectin to all subjects. Only after completion of all the procedures of the 6-month follow-up visit, and after nodulectomy and negative pregnancy test. It can also be administered at the early termination visit at the discretion of the Investigator. Ivermectin will also be available for administration as Rescue Medication, at the Investigator's discretion, in the event of clinically significant worsening of symptoms and/or signs related to onchocerciasis at any time during the study.18.AE monitoring will be performed as specified in Section 9.3.4 and will include scheduled questioning at the indicated time-points.

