#### 10.2.1 Treatment-Emergent Adverse Events

Treatment-emergent AEs are defined as any AE with the onset date that is after the first dose of study drug and no more than 30 days after the last dose. Events with the same onset date as the study drug start date are assumed to be treatment-emergent. All treatment-emergent AEs will be summarized overall, as well as by primary MedDRA SOC and Preferred Term. The SOCs will be presented in alphabetical order, and the PTs will be presented in alphabetical order within each SOC. The number and percentage of subjects experiencing treatment-emergent AEs will be summarized.

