#### 10.2.4 SAEs (Including Deaths) and Adverse Events Leading to Study Drug Discontinuation

Treatment-emergent SAEs (including deaths) and AEs leading to study drug discontinuation (ABBV-4083, albendazole, ABBV-4083 and albendazole, and

ABBV-4083 and/or albendazole) will be summarized by SOC and PT and in listing format. Listings of all SAEs and all deaths during the study will also be provided.

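### Non-serious adverse events that start more than 30 days after the last dose are collected in Part 1 but appear in no planned table or listing

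*SAP*

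**What the plan says.** **Endpoint.** SAP 3.4 bases the safety endpoints on a set of assessments, the first being "Adverse Event (AE) assessment (all reported AEs"). Protocol 5.5 gives the same scope.

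**Collection.** Protocol 9.3.4.5 states that "all non-serious AEs will be reported from administration of the first intake of IMP until the subject's end of study participation". The Part 1 schedule (protocol Appendix 1, Table 7) has adverse-event monitoring at Month 3, Month 6 and the end-of-study visit.

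**Analysis.** SAP 10.2.1 defines a treatment-emergent event by an "onset date that is after the first dose of study drug and no more than 30 days after the last dose". The overview rows, the tables by system organ class and preferred term, and the discontinuation summaries in SAP 10.2.2 to 10.2.4 are built on that definition. Protocol 10.8 sets the same limit: "The number and percentage of subjects experiencing TEAEs will be tabulated using MedDRA system-organ class and preferred term".

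**What goes past the limit.** The overview in SAP 10.2.2 counts all deaths, with a separate category for those more than 30 days after the last dose. SAP 10.2.4 adds: "Listings of all SAEs and all deaths during the study will also be provided".

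**Month 6.** All Part 1 subjects are to receive ivermectin after the Month 6 nodulectomy (SAP 2.2). Protocol 8.3 says that this ivermectin is not an IMP, so it does not restart the 30-day clock.

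**The concern.** The collection window and the analysis window differ by several months, and no output covers the difference for non-serious events. Protocol 9.3.4.6 stresses that severe and serious are different things. A Grade 3, drug-related, non-serious event starting on Day 60 would be in the database but in no planned table or listing.

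Part 1 safety is part of the basis for choosing the Part 2 regimens (protocol 10.9). Two kinds of late event bear on that choice:

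- **Reactions to Month 6 ivermectin.** Protocol 3.5.1.4 says a Mazzotti reaction may occur and links it to antigens from microfilariae and *Wolbachia*, which are what the test regimens are meant to affect. Arm K in Part 2 gives a selected regimen followed by ivermectin at Month 6, and Part 1 yields data on that sequence first.
- **Wound events after nodulectomy.** The end-of-study visit is scheduled for wound care and adverse-event questioning.

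**Working it through.** **1. End of the analysis window.** Protocol Appendix 1, Table 7, footnote 17: "IMPs will be administered daily from D0 to D13 on site". The last dose, active or matching placebo, is on Day 13 in every arm. 13 + 30 = Day 43. Protocol 6.1, inclusion criterion 4, gives the same day as one month after the final Part 1 intake, so the plan's own figure is reproduced.

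**2. Length of follow-up.** Protocol Synopsis, Study Duration: "In Part 1: each subject's participation will last approximately 6½ months" after screening. 6.5 × 30.44 = 197.8 days.

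**3. Share of follow-up time outside the window**, (T − 43)/T:

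| Assumption for T | T (days) | Outside |
|---|---|---|
| 6.5 months × 30.44 | 197.8 | 154.8/197.8 = 78.3% |
| 6.5 months × 30 | 195 | 152/195 = 77.9% |
| Month 6 + 14 days | 196.6 | 153.6/196.6 = 78.1% |
| Month 6 visit 1 month early, end of study the same day | 152.2 | 109.2/152.2 = 71.7% |
| Month 6 visit 1 month late, end of study 28 days later | 241.1 | 198.1/241.1 = 82.2% |

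If the clock ran from the last active dose in Arms A, C, D and E (Day 6), the window would close on Day 36 and the share would be (197.8 − 36)/197.8 = 81.8%.

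**4. Visits.** The earliest permitted Month 3 visit is 3 × 30.44 − 7 = Day 84, and the earliest Month 6 visit is 5 × 30.44 = Day 152. Every scheduled visit after the in-house period falls after Day 43.

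**5. Other outputs that reach past Day 43.**

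- *Eye and skin.* SAP 9.5 summarises graded ocular and skin outcomes by arm at Month 3 and Month 6. Footnotes 18 and 23 to Table 7 put nodulectomy and ivermectin after the other Month 6 procedures, and the end-of-study column shows no eye or skin examination. These summaries therefore describe the state before the Month 6 procedures.
- *Laboratory and vital signs.* SAP 10.3 and 10.4 summarise them at Month 3 and end of follow-up, and vital-sign criteria use all post-baseline values. Table 7 schedules neither at Month 6 nor at the end-of-study visit.
- *Serious events.* SAEs and deaths are listed for the whole study.

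After the scheduled Month 6 procedures, adverse-event questioning is thus the main planned source of safety information, and its non-serious part has no output.

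**The case against.** The case on the other side has five parts.

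- *SAP 3.4 names data sources, not an analysis window, and protocol 10.8 uses the same 30-day rule.* This stands in part. A reader might infer that the SAP departs from the protocol. It does not: the mismatch between endpoint and outputs is in both documents. The gap remains on either reading, and protocol 10.8 leaves the details of the safety analysis to the SAP.
- *Other wording is broader or narrower.* SAP 10.2 opens by saying, without restriction, that adverse events will be summarised, and protocol 9.3.4.5 also has a sentence limited to treatment-emergent events. Neither supplies an output for a late non-serious event, and the explicit rule for non-serious events in 9.3.4.5 runs to the end of participation.
- *Much late safety content is analysed elsewhere.* This stands for graded eye and skin findings, laboratory values and vital signs, within the limits in step 5 of the working. They are not adverse-event outputs and carry no relatedness.
- *Day 43 is far beyond exposure.* Protocol 3.5.2.2 gives half-lives under 4 hours for ABBV-4083 and 8 to 12 hours for albendazole sulfoxide, and its adverse-event toxicity criteria also stop at 30 days. This justifies keeping the treatment-emergent tables as the main analysis. It does not cover events tied to a slow parasitological effect or to the Month 6 procedures.
- *The DSMB sees non-serious events during the study, and regimen selection uses all available data.* True, but the recommendation on Part 2 rests on the final unblinded analyses (SAP 11.1), where these events have no planned output.

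A reader might also infer that reactions to Month 6 ivermectin will differ by arm. That is possible but conjectural: every arm receives it, and the protocol gives no figure.

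**Conclusion.** The point holds as a gap in the planned outputs. In Part 1, a non-serious adverse event with onset after about Day 43 is collected but neither tabulated nor listed under the SAP. The uncovered period is about 78% of follow-up time, or roughly 72% to 82% across the visit windows. This assumes last intake on Day 13 and participation of about 6.5 months.

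Three stronger readings are not supported:

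- That 78% of non-serious events are lost. The documents give no event rate. Dosing and the frequent in-house questioning fall inside the window, so the share of events could be well below the share of time.
- That these events are never reported, or that every adverse-event table stops at 30 days. The protocol uses reporting to mean collection in source documents and the eCRF, and that happens. The deaths row and the SAE and death listings run to the end of study.
- That every event after nodulectomy or ivermectin is missed. This is so for non-serious events after the scheduled Month 6 procedures. Either procedure at an early termination visit could fall inside the window.

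The primary efficacy result is unaffected. What is affected is the completeness of the safety evidence for choosing Part 2 regimens.

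**What to change.** Keep the treatment-emergent tables in SAP 10.2 as they are, and add:

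1. One table by arm of adverse events with onset more than 30 days after the last dose, by system organ class and preferred term, with maximum grade and relatedness handled as in SAP 10.2.3. Show events after the Month 6 nodulectomy and ivermectin separately from earlier ones, with the number of subjects who had those procedures as denominator, and state a rule for onset on the same day.
2. One listing of the same events.
3. One row in the SAP 10.2.2 overview for all adverse events through end of study.

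Restating the endpoint as treatment-emergent events plus all SAEs and deaths would remove the inconsistency in wording, but would leave the late non-serious events without an output.

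The cost is one extra table, one listing and one overview row, from data already collected. No change to visits, data capture or the treatment-emergent definition is needed.

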## 4.0 Analysis Populations

The following population sets will be used for the analyses.

The Intention-to-Treat (ITT) population includes all randomised subjects who received at least one dose of study drug. The ITT population will be used for all non-primary efficacy estimands. Subjects will be included in the analysis according to the treatment arm to which they were randomised.

The Per-Protocol (PP) population will include all ITT subjects who had Month 6 nodulectomy (ND6M) with live female adult worms, who completed treatment and did not take prohibited medication(s) during the study. Treatment completion is defined as taking at least 6 out of 7 days of ABBV-4083 in Arm A, 12 out of 14 days of ABBV-4083 in Arm B, 6 out of 7 days of ABBV-4083 + albendazole in Arm C, 6 out of 7 days of ABBV-4083 and all 3 days of albendazole in Arm D, and 6 out of 7 days of albendazole in Arm E. Prohibited medications (Appendix B) include those with anti-filarial or anti-*Wolbachia* effect taken at any time during the study, or strong CYP3A inducers or dexamethasone taken during the treatment period. The PP population will be used as the primary population for testing the two primary hypotheses (Section 2.1).

The Safety population includes all randomized subjects who received at least one dose of study drug. Subjects will be included in the analysis according to treatment as randomized. The Safety population is the same as the ITT population.

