# 10.0 Safety Analyses

#### 10.1 General Considerations

Safety data will be summarized for the Safety population in Part 1. If any of Arms A B C, D was closed during the study and any of Arms F, G, H, I was opened, all individual treatment arms will be included in the safety analyses. All safety summaries will be presented by treatment arm, as well as for all subjects taking ABBV-4083 (i.e., combining Arms A, B, C, D, as well as, F, G, H, I, if applicable). For the safety analyses, a subject's treatment arm will be determined based on the treatment arm assigned at randomization.

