#### Table 2.SAP Version History Summary

Version	Date	Summary
		• Section 3.2 and Section 9.4.2 Secondary endpoint of status of each live female adult worm as without Wolbachia assessed by PCR at Month 6 has been changed to status of each nodule containing at least one live female adult worm as without Wolbachia assessed by PCR at Month 6 due to a change in PCR data availability.
		• Section 3.4 For safety endpoints, removed physical, skin, and ophthalmological examination findings since they are summarized as the secondary efficacy endpoints.
		• Section 3.4 For safety endpoints, removed urine analysis because only abnormal results are collected.
		• Section 4.0 and Section 10.1 Updated safety analysis arms to be determined by the subject's randomized arm to align with treatment regimens under study.
		• Section 5.0 Subject disposition summary for completed protocol-specified treatment, prematurely discontinued study drug, reason for discontinuation of study drug, interruption of study drug, and reason for interruption of study drug were clarified to include summaries by study drug.
		• Section 6.0 Study drug duration categorical summary was updated to add the category of "> 14 days."
		• Q1, Q3 were added to all numerical summaries that included calculation of the median.
		• Section 7.1 and Section 9.6 For demographics and baseline characteristics, categories for number of operable sites with onchocercomata, number of palpated nodules, and number of previous ivermectin rounds were updated to be 0, 1, >1. Also, number of years resident in endemic area was added, and for summary of symptoms of onchocerciasis disease, "other" category was removed.
		• Section 7.3 Summaries of prior and concomitant procedures were removed because they are collected as text fields. Anthelmintic medications taken prior to the start of study drug were removed from the summary of concomitant medications because by definition these medications were only taken prior to start of study drug.
		• Section 8.0 and Section 9.2 Clarified the conditions which lead to data imputation.
		• Section 9.1 Clarified that no adjustment for multiple comparisons would be made.

Version	Date	Summary
		• Section 9.5 Clarified that the decline in number of Wolbachia , as assessed by PCR, would be assessed using the ratio of PCR copy number of Wolbachia signal to PCR copy number of worm signal.

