#### Appendix A. Protocol Deviations

Protocol deviations include eligibility criteria violations, receipt of wrong treatment or incorrect dose of study treatment, development of withdrawal criteria without being withdrawn, use of prohibited concomitant medications, and Month 6 nodulectomy not performed. A listing of subjects with protocol deviations will be provided.

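### Part 1 safety tables group subjects strictly by randomised arm, so a control subject who took ABBV-4083 would count as a control and be missing from the ABBV-4083 column

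*SAP*

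**What the plan says.** SAP 4.0 defines the Safety population as randomised subjects with at least one dose and adds: "Subjects will be included in the analysis according to treatment as randomized". It also states: "The Safety population is the same as the ITT population". SAP 10.1 repeats the rule for all safety work: "For the safety analyses, a subject's treatment arm will be determined based on the treatment arm assigned at randomization".

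SAP 10.1 then describes the columns: "All safety summaries will be presented by treatment arm, as well as for all subjects taking ABBV-4083 (i.e., combining Arms A, B, C, D", plus Arms F-I if they are opened. The pooled column carries an exposure label but is defined by combining arms, and arm means randomised arm.

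SAP Appendix A counts "receipt of wrong treatment or incorrect dose of study treatment" among the protocol deviations and provides a listing. No safety table is given by treatment received, either as main or as sensitivity analysis.

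The rule was chosen on purpose. The SAP version history (Table 2) records for version 2.0: "Updated safety analysis arms to be determined by the subject's randomized arm to align with treatment regimens under study". Protocol 10.2 and 10.8 define the Safety population by receipt of IMP and do not say to which arm a misdosed subject belongs.

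**The concern.** A safety comparison asks what happened to people who took the drug against people who did not. Under the stated rule, an Arm E subject given active ABBV-4083 stays in the control column of every Part 1 safety summary and is absent from the pooled ABBV-4083 column. Any harm the drug caused in that subject would appear as a control event. A subject in Arms A-D who took no ABBV-4083 would dilute the pooled column. If the drug does cause harm, both errors shrink the apparent difference.

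The stake is specific. Protocol 2.3.2 and 3.5.1.1 name altered liver tests as the one potential safety effect under consideration. SAP 10.3 estimates laboratory changes from baseline for each active arm, and for A-D together, against Arm E. Under Protocol 10.9 and SAP 11.1, the unblinded Part 1 results inform whether to proceed to Part 2 and with which regimens.

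**Working it through.** No stated sample size, power or alpha depends on this rule, so there is no plan figure to reproduce. The check has two parts: what the rule does to one subject, and how many subjects it could reach.

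**Inputs from the documents**
- 30 subjects per arm, 150 in total (SAP 2.2), so 30 in Arm E and 4 × 30 = 120 in Arms A-D.
- Three dispensings per subject, on D0, D3 and D7, through the IRT (Protocol Table 7, footnote 17).
- Active ABBV-4083 is given on Days 0-6 in Arms A-D and on Days 7-13 in Arm B only (SAP 2.3).

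**Assumption.** The documents give no wrong-kit rate. I use 0.2% to 1% per dispensing.

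**1. Effect per misdosed control.** Suppose m Arm E subjects received ABBV-4083, all had the event, and nobody else did.

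| m | Arm E, as randomised | Pooled, as randomised | Arm E, by exposure | Pooled, by exposure |
|---|---|---|---|---|
| 0 | 0/30 = 0% | 0/120 = 0% | 0/30 = 0% | 0/120 = 0% |
| 1 | 1/30 = 3.3% | 0/120 = 0% | 0/29 = 0% | 1/121 = 0.8% |
| 2 | 2/30 = 6.7% | 0/120 = 0% | 0/28 = 0% | 2/122 = 1.6% |
| 3 | 3/30 = 10.0% | 0/120 = 0% | 0/27 = 0% | 3/123 = 2.4% |

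For m = 1 the difference, pooled minus control, is -3.33 points as randomised and +0.83 points by exposure: a swing of 4.16 points and a change of sign. This is a worst case, because the misdosed subject must also have the event. If the event rate on drug were 10% (an assumption), the expected shift in the Arm E rate for m = 1 would be 0.10/30 = 0.33 points.

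**2. Expected number of misdosed controls**
- Arm E dispensings: 30 × 3 = 90.
- Upper bound, if every wrong Arm E kit were active: 90 × 0.002 = 0.18 to 90 × 0.01 = 0.9 subjects.
- If a wrong kit is drawn at random from the other 149 subjects, it is active with probability 120/149 at D0 and at D3, and 30/149 at D7. Expected number = 30 × (2 × 120/149 + 30/149) × rate = 54.4 × rate, which gives 0.11 at 0.2% and 0.54 at 1%.

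**3. The reverse error.** A subject in Arm A, C or D takes active drug from two dispensings (D0 and D3), and a subject in Arm B from three. One wrong kit therefore leaves the subject exposed and correctly in the pooled column. To be unexposed takes at least two errors. If errors were independent, this would be at most 120 × 0.01² = 0.012 subjects at the higher rate. A whole-course swap would also do it, but the documents give no rate for that.

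**The case against.** The strongest reply is that misdosing should be rare and would be visible. Allocation is central through the IRT, and dosing is on site and directly observed (Protocol 7.3, 7.6, 9.2.3). Drug levels are measured. Medication errors must be documented as deviations (Protocol 9.3.4.11). SAP 10.2.4 and 10.3 give subject-level listings for SAEs, discontinuation AEs, laboratory values that rise to Grade 3 or higher, and all liver values of anyone who crosses a hepatotoxicity threshold. The rule is deliberate and disclosed, and the protocol synopsis calls the safety analysis descriptive.

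Much of this stands. The documents report no dispensing error, and a careful reader could find a misdosed subject by cross-reading listings. Some of it does not. Observation shows that a capsule was swallowed, not what it held: active and placebo capsules look alike (Protocol 7.4.1). The compliance summary in SAP 6.0 counts ABBV-4083 and its placebo together, so an Arm E subject on active capsules could show full compliance. The version 2.0 rationale fits a subject who stops early and stays in the assigned regimen; it does not cover an exposed subject shown as unexposed.

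Three stronger readings are tempting, and the documents do not support them.
- A reader might multiply all 450 dispensings by 0.2% to 1% and infer that 1 to 5 subjects (0.9 to 4.5) are affected. That counts wrong kits in every arm, including swaps between active arms that touch neither Arm E nor the pooled column.
- A reader might infer that one wrong kit makes an A-D subject unexposed. The D0, D3 and D7 schedule rules that out.
- A reader might infer that the Part 1 safety comparison is in fact biased. Nothing shows that any subject was misdosed.

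**Conclusion.** The point holds as a conditional weakness in the stated rule. By its text, the SAP would count an ABBV-4083-exposed control as unexposed throughout the Part 1 safety tables, and the pooled column's label promises exposure while its definition uses allocation. The expected reach is small: about 0.1 to 0.5 Arm E subjects, at most 0.9, on an assumed wrong-kit rate of 0.2% to 1%, with random draws behind the central figures. The consequence of a single case is not negligible, because one misplaced event is 1/30 = 3.3 points in Arm E and is lost from the pooled count. The conclusion is limited to Part 1, since SAP 1.0 leaves Part 2 to a separate plan. The change is worth making because it is cheap, not because an error is known.

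**What to change.** In SAP 4.0 and 10.1, keep the randomised arm as the default for safety and state that missed doses or early stopping do not change it. Then add two exceptions:
- An Arm E subject who received at least one dose of active ABBV-4083 is removed from Arm E and counted only in the pooled ABBV-4083 group.
- A subject randomised to Arms A-D or F-I who received no active ABBV-4083 is removed from the pooled group.

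Footnote each reassigned subject, leave ITT as randomised, and set the rule before unblinding.

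Assigning subjects by the regimen that matches most doses would be worse. An Arm E subject with one wrong D0 kit (Days 0-2, 3 of 14 days) would stay in Arm E by majority. If any intake also placed that subject in the pooled group, the subject would sit on both sides of the comparison. A wrong D7 kit from Arm B would give a 7-to-7 day tie. The any-dose rule avoids both problems.

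The cost is a short assignment rule and one derived variable. If anyone is reassigned, safety denominators will differ slightly from ITT, and the SAP 4.0 statement that the two populations are the same will need a qualifier on arm assignment. With no dispensing errors, every table is unchanged.
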